# 9.1.2. Index Date and Follow-Up

The index date will be the date of the eligible initiation of ritlecitinib, baricitinib or another approved systemic treatment for AA during the cohort accrual period, as recorded in the data sources. Follow-up will start on the date after the index date and continue until the earliest of disenrollment from the data source, an event of interest, or censoring.

# 9.2. Setting

This study will use population-based secondary data sources from Denmark, France, and Sweden. All three study countries have universal healthcare, whereby routinely collected data continuously accrue in the participating nationwide databases (described in Section 9.4). Loss to follow-up is expected to be minimal and primarily due to emigration, which is expected to be low. Studies based on secondary electronic healthcare data sources are efficient for monitoring rare events and events that require long-term follow-up, when these types of events are well captured in the data source.

These large real-world data sources are expected to allow robust assessment of the safety events of interest. Most proposed safety events of interest are likely to be well captured in the data sources, as the majority of the events require immediate treatment in either a hospital or specialized outpatient setting. Furthermore, safety events such as thromboembolic events have been shown to have high positive predictive values in the Danish and Swedish national registries (20).

### 9.2.1. Inclusion Criteria

Patients must meet all of the following criteria to be eligible for inclusion in the study:

- 1. Have a record of at least one dispensing or hospital administration (hereafter collectively referred to as dispensing) of ritlecitinib, baricitinib, or other approved systemic AA treatment during the cohort accrual period.
- 2. Have a diagnosis of AA on or up to 5 years before the index date, recorded during a hospital/specialist clinic encounter or by AA noted as the indication on an outpatient pharmacy dispensing record (whenever indication is captured). Treatment proxies may be considered if relevant for a data source and sufficiently specific for AA (21).

### 9.2.2. Exclusion Criteria

Patients meeting any of the following criteria, applied in the order listed, will not be included in the study:

- 1. Age less than full 12 years on the index date
- 2. Less than 12 months presence in the data source, due to residence in a given country
- 3. A previous record of the agent dispensed on the index date at any time on or up to 5 years before the index date

Figure 1 shows the study design schema.

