Baricitinib is the only other systemic therapy approved for AA (approved in June 2022). Baricitinib's other indications in the EU are moderate to severe active rheumatoid arthritis in adult patients who have responded inadequately to, or who are intolerant to one or more disease modifying anti rheumatic drugs; moderate to severe atopic dermatitis in adult and paediatric patients 2 years of age and older who are candidates for systemic therapy; and active juvenile idiopathic arthritis in patients 2 years of age and older who have had an inadequate response or intolerance to one or more specific prior conventional synthetic or biologic disease modifying anti rheumatic drugs (15).

According to the treatment guidelines of the Danish Dermatological Society, updated in July 2023, systemic treatment for AA can be considered in patients meeting all of the following criteria: (1) established AA diagnosis; (2) disease duration >6 months without new lesions, but <8 years if a new lesion has been observed within an 8-year period; (3) severe AA, corresponding to hair loss covering more than 50% of the scalp as measured with the Severity of Alopecia Tool (SALT) score; and (4) Dermatology Life Quality Index (DLQI)  $\geq$ 10. The 2023 guidelines cite baricitinib, 4 mg daily, as the best documented treatment, following the necessary workup and observing the label restrictions. Baricitinib is indicated for adults, with special caution in patients 65 years of age or older, patients at increased risk of serious cardiovascular disease, patients with a history of smoking and patients at an increased risk of cancer or venous thromboembolism (VTE). The above guidelines require that the effect of systemic treatment be continuously assessed at 3, 6, 9 and 12 months, and

PFIZER CONFIDENTIAL

CT24-WI-GL02-RF02 5.0 Non-Interventional Study Protocol Template For Secondary Data Collection Study 01-Aug-2023

*O1-Aug-2023* Page 12 of 47

that the treatment be discontinued if both of the following efficacy targets are not achieved after 36 weeks of treatment: (1) SALT score <20% and (2) DLQI <5 (16). However, as of 24 January 2024, the Danish Medical Council (Medicinrådet) no longer recommends baricitinib treatment for severe AA. The Council recommends systemic treatment with combination of methotrexate and prednisolone as the best documented treatment, recommended for patients with long-term widespread disease following a thorough workup (17).

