### Figure 1. Study Design Schema

```
Cohort accrual period [15 September 2023 – 14 September 2031]
(First dispensing of ritlecitinib, baricitinib or another approved systemic AA treatment)
Day 0 = index date in a given exposure cohort
```

Diagnosis of Alopecia areata [-5 years, 0 days]	
Exclusion: age <12 years on index date [0, 0]	
Exclusion: minimal residence [-365 days, -1 day]	
Washout period to define new users [-5 years, -1 day]	
	Follow up Window Days (1, Censor a ]

a. Earliest of: outcome of interest, or censoring by discontinuation/switch, death, disenrollment, end of the study period on 15 September 2033.

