### 9.3. Variables

### 9.3.1. Exposure

Exposure cohorts will be defined based on the type of treatment dispensed on the index date. The following 3 exposure cohorts will be defined:

- 1. Ritlecitinib cohort
- 2. Baricitinib cohort
- 3. Other approved systemic AA treatment cohort (if used)

The eligible treatment initiated on the index date will be referred to as the index treatment. The exposure will continue until the end of a 90-day grace period following the estimated discontinuation of the index treatment. Discontinuation may result either by stopping the index treatment or initiation (switching to) another study treatment. Duration of each dispensing will be computed based on days supplied, estimated based on assumed daily dose, package size, and number of packages in each dispensing. Dispensings less than 90 days apart will represent a continuous treatment period. Definitions, including duration of the grace period, may be slightly modified if otherwise indicated by the data.

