### 9.7.3. Analyses of the Exploratory Objective

An exploratory comparative analysis estimating hazard ratios of the safety events of interest among AA patients treated with ritlecitinib compared with patients treated with baricitinib or other systemic treatment will be conducted for the final report only, study size permitting. This analysis will use Cox's proportional-hazards regression to estimate HRs and 95% CIs. To account for potential confounding in the comparative analysis, a propensity-score based method, such as inverse-probability treatment weighting (IPTW) will be used to balance measured characteristics of the exposure cohorts being compared (51). The covariate balance between the exposure cohorts (before and after IPTW) will be evaluated using standardized differences for continuous covariates and standardized differences of proportion for each (non-missing) category for categorical covariates. Characteristics with standardized differences greater than 0.10 after weighting will indicate imbalance and will be adjusted for in the comparative analyses. If IPTW is applied, robust variance estimators will be used to address lack of independence between patients induced by weighting. The extent of unmeasured confounding will be assessed using the E-value method (52, 53). Full details of the methods will be provided in the SAP.

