# 9.7.4. Subgroup Analyses

If study size permits, the following analyses will be conducted for the subgroups listed below: descriptive characteristics by exposure cohort, IRs by exposure cohort, and HRs for comparative analyses.

- Sex (male, female)
- Adolescent and adult populations, based on age on index date (12-17 years, 18 years and older)
- Prior systemic therapy
- To allow for sufficient follow-up for outcomes with long induction or latent periods, subgroup analyses will be conducted among the subset of patients with a minimum of 5 years of follow-up, defined as patients initiating the study treatments between 15 September 2023 and 14 September 2028.

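### The washout covers only the index agent, so patients switching from baricitinib enter the ritlecitinib cohort while prior baricitinib use is impossible in the baricitinib cohort, and the weighting named for the hazard ratio cannot balance it

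*Protocol*

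**What the plan says.** Exclusion 3 in section 9.2.2 removes a patient with "A previous record of the agent dispensed on the index date at any time on or up to 5 years before the index date". The design schema (Figure 1) defines "Day 0 = index date in a given exposure cohort", so the index date is set cohort by cohort. Nothing in 9.2.1 or 9.2.2 requires a patient to be new to the other study treatments.

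The protocol expects switching: under 9.3.1, "Discontinuation may result either by stopping the index treatment or initiation (switching to) another study treatment". Section 9.3.3 lists earlier AA therapies, and other JAK inhibitors, among the characteristics measured over the 5 years to the index date.

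For the exploratory comparison, section 9.7.3 names a propensity-score method, with inverse-probability weighting as its example. It adds: "Characteristics with standardized differences greater than 0.10 after weighting will indicate imbalance and will be adjusted for in the comparative analyses". Section 9.7.4 lists "Prior systemic therapy" as a subgroup for incidence rates and hazard ratios, if size permits. None of the sensitivity analyses in 9.7.5 is restricted to patients naive to all study treatments.

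**The concern.** A washout on the index agent alone leaves prior use of the other drug free to differ between cohorts, and here it must differ. Prior baricitinib can occur among ritlecitinib initiators but is excluded, within the lookback, among baricitinib initiators. In mirror image, prior ritlecitinib can occur only among baricitinib initiators.

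In practice the mixing may run mainly one way. Section 7 dates baricitinib's approval for AA to June 2022, about 15 months before accrual opens on 15 September 2023. Patients who started baricitinib in that interval are barred from the baricitinib cohort for the length of the washout but may enter the ritlecitinib cohort.

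The hazard ratio would then compare a group that is partly second-line with one in which nobody has already used that comparator. Switchers are also selected. Section 9.7.2 drops patients with the respective prevalent condition, so those who remain after baricitinib came through it without a recorded event. For the primary objective, the ritlecitinib rates would mix naive and switched patients, with standardization for age and sex only.

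**Working it through.** **Inputs.** From 9.5: 835 ritlecitinib patients, 3,864 person-years per cohort, 7,728 in total at 1:1, and a malignancy rate of 1.13 per 1,000 person-years (Table 3). From 9.7.3: the 0.10 limit. Assumed: f, the share of ritlecitinib initiators with baricitinib in the previous 5 years. The protocol gives no value, so a range is shown.

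**1. The plan's own figure.** Expected malignancies are 7,728 × 1.13/1,000 = 8.73. The protocol states neither alpha nor power. Two-sided 0.05 and 80% power reproduce its figure with the Schoenfeld formula: HR = exp[(1.960 + 0.842)/√(0.25 × 8.73)] = 6.66, stated as 6.7.

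**2. Imbalance before weighting.** For a share f against 0, the standardized difference is f/√(f(1−f)/2) = √(2f/(1−f)).

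**3. Imbalance after weighting to the combined population, 1:1 cohorts, this one covariate.**
- Patients with prior baricitinib are all in the ritlecitinib cohort, so their propensity is 1 and their weight is 1. Their total weight, per ritlecitinib patient, is f.
- Among naive patients the propensity of ritlecitinib is (1−f)/(2−f). Naive ritlecitinib patients therefore carry total weight (1−f) ÷ [(1−f)/(2−f)] = 2−f.
- The weighted share with prior baricitinib is f/[f + (2−f)] = f/2 in the ritlecitinib cohort and 0 in the baricitinib cohort.
- With p = f/2, the weighted standardized difference is √(2p/(1−p)) = √(2f/(2−f)).

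| Assumed f | Unweighted | Weighted |
|---|---|---|
| 10% | 0.47 | 0.32 |
| 20% | 0.71 | 0.47 |
| 30% | 0.93 | 0.59 |

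Setting √(2f/(2−f)) = 0.10 gives f = 0.02/2.01, about 1%, or roughly 8 of 835 patients. Above that share the weighted difference exceeds the limit.

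**4. Prior JAK-inhibitor use as a class.** If 30% of the ritlecitinib cohort and an assumed 5% or 10% of the baricitinib cohort have used some earlier JAK inhibitor, the same weighting equalizes the shares. They become 17.5% in both cohorts, or 20% in both, with weights of 7.0 or 4.0 for the exposed baricitinib patients. Only the drug-specific covariate lacks overlap.

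**5. What restriction costs.** The minimum detectable malignancy HR, from the formula in step 1 with allocation a, is exp[2.802/√(a(1−a) × events)].

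| Assumed f | Only ritlecitinib cohort shrinks | Both shrink, 1:1 |
|---|---|---|
| 0 | 6.7 | 6.7 |
| 10% | 7.0 (8.3 events, a = 0.9/1.9) | 7.4 (7.9 events) |
| 30% | 8.1 (7.4 events, a = 0.7/1.7) | 9.6 (6.1 events) |

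Events are 3,864 × (2−f) × 1.13/1,000 in the first case and 7,728 × (1−f) × 1.13/1,000 in the second.

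**The case against.** The defence has several good points.

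- **The method is not fixed.** Section 9.7.3 gives inverse-probability weighting as an example and leaves details to the SAP. Overlap weights, matching or trimming would drop patients whose propensity is 1, so a reader who infers that no propensity method can cope goes too far. It also goes too far to say that weighting leaves the difference unchanged, since step 3 shows it falls. What stands is that the one method named does not reach the protocol's own limit.
- **The adjustment rule is a partial remedy.** With a prior-baricitinib term in the Cox model, the treatment effect is estimated from baricitinib-naive patients, provided there is no interaction. Switchers then add nothing to the contrast, which argues for saying so openly.
- **The subgroup contains a like-for-like contrast.** Its stratum without prior systemic therapy would serve, if it is run. But it is conditional on size, the protocol does not say which drugs count as systemic, and the other stratum remains mixed.
- **Carry-over is limited.** A reader might infer that cancers induced under baricitinib will count against ritlecitinib. Section 9.7.2 excludes prevalent conditions and allows early post-index events to be disregarded, with 12 months for malignancy according to 9.7.5. Only cancers surfacing later could be counted that way.
- **The switcher share is unknown.** Section 7 points both ways: baricitinib is first-line for severe adult disease in France, the Danish Medical Council stopped recommending it in January 2024, and its AA use is in adults whereas ritlecitinib starts at age 12.
- **The comparison is exploratory**, reserved for the final report and conditional on size. That limits the weight of the point but does not remove it.

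**Conclusion.** The point holds for prior baricitinib and, mirrored, for prior ritlecitinib. Each is a structural zero in one cohort, and the weighting named in 9.7.3 leaves a standardized difference of about 0.32 to 0.59 for assumed switcher shares of 10% to 30%. This rests on 1:1 cohorts, a single covariate and an assumed share. The figures measure imbalance; the direction and size of bias in the hazard ratio cannot be derived from the protocol.

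Three wider readings are not supported. Prior JAK-inhibitor use as a class is not beyond balancing, because it can occur in both cohorts. The zero applies to recorded use within the lookback only: 9.2.2 requires just 12 months in the data source, so earlier use can go unseen. And the inclusion of the index date itself in exclusion 3 is a matter of wording, since the text speaks of a previous record and Figure 1 ends the washout the day before.

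The primary incidence rates remain valid descriptions of their cohorts, but are harder to read while naive and switched patients are merged. This is an inexpensive improvement worth making, not a fault that undermines the study.

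**What to change.** In 9.7.3, confine the exploratory hazard ratio to patients with no record of any study treatment (ritlecitinib, baricitinib or another approved systemic AA drug) in the 5 years to the day before index. At minimum, add that restriction as a prespecified analysis in 9.7.5. In 9.7.2, keep switchers in the primary incidence rates but report each cohort by naive versus switched from another study treatment.

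The data are already planned for collection, so the work is protocol and SAP wording plus one stratum in the rate tables. The price is a smaller set for an already imprecise hazard ratio, as shown in step 5. The stratified rate tables will also have small cells, and 9.10 masks counts of 1 to 4.

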### Figure 1. Study Design Schema

```
Cohort accrual period [15 September 2023 – 14 September 2031]
(First dispensing of ritlecitinib, baricitinib or another approved systemic AA treatment)
Day 0 = index date in a given exposure cohort
```

Diagnosis of Alopecia areata [-5 years, 0 days]	
Exclusion: age <12 years on index date [0, 0]	
Exclusion: minimal residence [-365 days, -1 day]	
Washout period to define new users [-5 years, -1 day]	
	Follow up Window Days (1, Censor a ]

a. Earliest of: outcome of interest, or censoring by discontinuation/switch, death, disenrollment, end of the study period on 15 September 2033.

### 9.3. Variables

### 9.3.1. Exposure

Exposure cohorts will be defined based on the type of treatment dispensed on the index date. The following 3 exposure cohorts will be defined:

- 1. Ritlecitinib cohort
- 2. Baricitinib cohort
- 3. Other approved systemic AA treatment cohort (if used)

The eligible treatment initiated on the index date will be referred to as the index treatment. The exposure will continue until the end of a 90-day grace period following the estimated discontinuation of the index treatment. Discontinuation may result either by stopping the index treatment or initiation (switching to) another study treatment. Duration of each dispensing will be computed based on days supplied, estimated based on assumed daily dose, package size, and number of packages in each dispensing. Dispensings less than 90 days apart will represent a continuous treatment period. Definitions, including duration of the grace period, may be slightly modified if otherwise indicated by the data.

### PFIZER CONFIDENTIAL

CT24-WI-GL02-RF02 5.0 Non-Interventional Study Protocol Template For Secondary Data Collection Study 01-Aug-2023 Page 17 of 47

### 9.3.2. Endpoints

The following endpoints (safety events of interest) will be assessed.

- Thromboembolic events, including:
  - VTE (including deep vein thrombosis [DVT] and pulmonary embolism [PE])
  - Arterial thrombosis (includes myocardial infarction [MI] and stroke)
- HZ
- Serious infections
- Opportunistic infections
- Incident primary malignancy, including:
  - Incident primary malignancy excluding nonmelanoma skin cancer (NMSC), overall and by major organ
  - Incident NMSC
- MACE\*, including (22):
  - o Nonfatal MI
  - Nonfatal stroke
  - Unstable angina
  - Hospitalization due to heart failure
  - Coronary revascularization by percutaneous intervention or coronary artery bypass graft
  - Cardiovascular death
  - \*Other MACE definitions (eg, excluding unstable angina, hospitalized heart failure, revascularization procedure) may be considered.
- Neurological events of interest (including the following events that are captured in at least one of the databases):
  - Peripheral neuropathy
  - Sensorineural hearing loss
  - o Migraine
  - Seizures and seizure disorders
  - Demyelinating disorders including multiple sclerosis
  - Neurodegenerative disorders
- Bone fractures

PFIZER CONFIDENTIAL

CT24-WI-GL02-RF02 5.0 Non-Interventional Study Protocol Template For Secondary Data Collection Study 01-Aug-2023 Page 18 of 47

- Growth metrics in adolescents
  - height and weight, conditional on sufficient data available beyond age 12 years (Denmark only)

### 9.3.3. Other Variables

The following demographic and clinical characteristics (as available in data sources) will be assessed among the members of the study population:

Demographics

- Age at index date
- Sex
- Calendar year of index date

AA characteristics

- Duration (to the extent possible to assess, e.g., since first recorded diagnosis in the available data)
- Severity (to the extent measurable in the data sources, e.g., by the intensity of AA-associated health care utilisation)

History of medication use, identified up to 5 years before and including index date

- Therapies for AA
- Potential off-label AA treatments such as corticosteroids (topical, oral, injected), diphencyprone, anthralin, topical minoxidil, methotrexate, dupilumab, other JAK inhibitors
- Medications that may modify risk for the endpoints
  - Low-dose aspirin
  - Non-aspirin non-steroidal anti-inflammatory agents (NSAIDs)
  - Anti-hypertensive medications
  - Lipid-lowering medications
  - Anticoagulants
  - Antiplatelets
  - Combined hormonal contraceptives (except France, no reimbursement)
  - Post-menopausal hormone replacement therapy
  - Anti-diabetic medications
  - Other immunosuppressants or biologics

History of comorbid conditions that are risk factors for the endpoints, identified on or before index date (to the extent measured in the participating data sources). The lookback period will be up to 5 years or as indicated by clinical rationale.

- Thromboembolic events (including VTE and arterial thrombosis)
- Stroke
- Diabetes
- Obesity (hospital diagnoses only, morbid obesity only)

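### The look-back for prior alopecia areata therapies includes the index date, so an any-use flag would be positive for every patient

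*Protocol*

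**What the plan says.** Section 9.3.3 gives one look-back for all medication covariates: "History of medication use, identified up to 5 years before and including index date". The first item under it is "Therapies for AA", with no exception for the drug that brings the patient into the study. A separate item covers off-label AA treatments and ends with "methotrexate, dupilumab, other JAK inhibitors". The list of risk-modifying medications ends with "Other immunosuppressants or biologics".

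Section 9.1.2 fixes day 0: "The index date will be the date of the eligible initiation of ritlecitinib, baricitinib or another approved systemic treatment for AA". Inclusion criterion 1 (Section 9.2.1) requires a record of such a drug. Exclusion criterion 3 (Section 9.2.2) bars earlier use of the same agent only, so a patient moving from one study drug to the other can enter the second drug's cohort.

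Figure 1 handles day 0 differently for new-user status: "Washout period to define new users [-5 years, -1 day"].

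For the exploratory comparison, Section 9.7.3 says that a propensity-score method "will be used to balance measured characteristics of the exposure cohorts being compared", with a standardized difference above 0.10 after weighting taken as imbalance. Section 9.7.4 lists "Prior systemic therapy" as a subgroup without giving a window.

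**The concern.** A treatment-history covariate should describe the patient before exposure starts. Here the window takes in the day on which exposure starts, and for one item the exposure is itself a member of the class being searched for. That item then records the study drug and not the history.

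What is lost is relevant to the comparison. Switching between study drugs is permitted, and a patient who has already taken the other one may differ in disease severity, treatment failure and cumulative immunosuppression from a patient who has taken neither. The AA-therapies item is the natural place to capture this. The off-label item does not clearly replace it, because both study drugs are approved for AA and so are not off-label there. At stake are the description of the cohorts, one confounder in the exploratory hazard ratios, and possibly the definition of one subgroup.

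**Working it through.** The protocol states no figure on this point, so there is none to reproduce. The check sets the rules side by side and then looks at what the balance diagnostic would show.

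**Step 1: what falls inside the window.**

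| Rule | Source | Day 0 |
|---|---|---|
| Medication history | Section 9.3.3 | included |
| Approved systemic AA drug started | Sections 9.1.2 and 9.2.1 | always, by definition |
| New-user washout | Figure 1 | excluded (ends day -1) |

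The first two rows together put at least one AA therapy in every patient's history. Exclusion criterion 3 has the same day-0 slip in its wording, and read literally it would remove everyone. Figure 1 settles that case, but nothing does the same for medication history.

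**Step 2: which items are affected.** The wording of the off-label and immunosuppressant items uses the word *other*, which sets the index drug apart. The AA-therapies item has no such word. Section 7 says that baricitinib is the only other systemic therapy approved for AA. If the item means approved therapies, in contrast to the off-label item beside it, it consists mainly of the study drugs. If it means any AA therapy, it is still positive for all.

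**Step 3: any-use coding.** For a binary covariate with prevalences p1 and p0, the standardized difference is

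(p1 − p0) / √{[p1(1 − p1) + p0(1 − p0)] / 2}.

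With day 0 counted, p1 = p0 = 1. Numerator and denominator are both 0, so the measure is undefined and cannot signal imbalance. With the window ended on day -1, under *assumed* prevalences of prior use:

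- 30% v 20%: 0.10 / √0.185 = 0.23
- 40% v 20%: 0.20 / √0.200 = 0.45
- 60% v 30%: 0.30 / √0.225 = 0.63

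All three would exceed the 0.10 threshold. If prior use were equal (50% v 50%), the value would be 0 and nothing would have been hidden.

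**Step 4: agent-level coding.** With day 0 counted, baricitinib history is 100% in the baricitinib cohort. Against *assumed* prior use in the ritlecitinib cohort:

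- 10%: −0.90 / √0.045 = −4.24
- 30%: −0.70 / √0.105 = −2.16
- 0%: the variance is zero and the flag separates the cohorts completely.

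The flag is then close to a copy of the exposure and unsuitable for a propensity model. Neither coding gives a usable covariate.

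**Step 5: what is not touched.** Section 9.7.2 plans crude and age- and sex-standardized incidence rates. Neither uses medication history.

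**The case against.** The strongest reply is that the item is headed as history, that Section 9.3.1 names the drug dispensed on day 0 the index treatment, and that no analyst would count the exposure as its own history. Section 9.3.4 leaves operational definitions to the SAP, which is not at hand, and no yes/no coding is stated. Much of this is fair, and a sensible programmer would probably correct the point. But the protocol does not leave the window open: it states one, with day 0 in it. The neighbouring items show that the authors separated out the index drug where they meant to.

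A reader might infer more than the text supports:

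- **That immunosuppressant history is also positive for everyone.** It is not. The wording "Other immunosuppressants or biologics" and "methotrexate, dupilumab, other JAK inhibitors" excludes the index drug, and no passage defines these covariates as a whole ATC class.
- **That the covariate would vanish from the propensity score without anyone seeing it.** Section 9.7.3 fixes no covariate list. Section 9.7.1 reports characteristics by cohort, so 100% everywhere would be visible. The standardized difference is undefined and not a passing zero, and agent-level separation would be conspicuous.
- **That the hazard ratios carry a bias of calculable size.** Such a figure would need prevalences and rate ratios that the protocol does not give. It would also assume the loss of information that the corticosteroid, methotrexate, dupilumab and immunosuppressant items still carry.
- **That the prior-systemic-therapy subgroup has an empty stratum.** That follows only if it is built on the Section 9.3.3 window, which no passage says, and the word *prior* points the other way.

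**Conclusion.** Wrong as written, with low severity. For "Therapies for AA" the stated window includes a day on which every patient has an approved AA drug. An any-use flag is therefore uninformative, and agent-level flags largely restate the exposure. This follows from the protocol's own definitions and needs no assumption. The standardized differences above do rest on assumed prevalences; they show only that real differences in prior use could exceed the protocol's threshold and go unmeasured by this item.

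The reach is limited to the cohort descriptions, the exploratory comparison (final report only, if size permits) and possibly one subgroup. Section 9.5 puts the minimum detectable hazard ratios for that comparison at 4.3 to 6.7 even with 835 ritlecitinib patients across the three countries, so it is already imprecise. The overall primary incidence rates are unaffected.

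**What to change.** In Section 9.3.3, for the AA-therapies item only, end the look-back on day -1 as Figure 1 does for the washout, or state that the index dispensing is not counted. Give the "Prior systemic therapy" subgroup in Section 9.7.4 the same explicit window. Carry both into the SAP.

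For the propensity score, the useful form is any prior approved systemic AA therapy other than the index agent. Exclusion criterion 3 makes same-agent history zero by design within each cohort, so agent-level flags would remain awkward even with the corrected window.

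Other comedications may keep day 0. The cost is one line in each place, with no extra data and no change to study size or to any stated figure.
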